5.8.4.2 Handling of Specimens

Tissues used for immunofluorescence analysis of PD-L1 expression and CD8 tumor infiltrating lymphocyte (TIL) will be fixed in 4% formalin for 24 hours, then transferred to 70% ethanol and stored at room temperature. Fixed tissue will be paraffin embedded and sectioned. CD8 TIL infiltration and PD-L1 expression will be assessed in appropriate sections by multiplex immunofluorescence (IF), performed by NIDCD Laboratory personnel in collaboration with LTIB Tissue Core personnel using standard IF staining techniques using Perkin-Elmer Opal staining kits, a Perkin-Elmer Vectra Polaris Image Analysis Platform and Perkin-Elmer inForm software. This platform has been validated for use in fixed human tissue analysis of CD8+ cell tissue infiltration and PD-L1 expression. ([21](#), [22](#))

5.8.4.3 Site Performing Correlative Study

[name] laboratory

5.8.4.4 Shipment of Specimens from the EET Biobank to Site Performing Correlative Study

Specimens will be shipped from the EET Biobank to:

Refer to Section [5.6.3](#).

5.8.4.5 Contact Information for Notification of Specimen Shipment

Refer to Section [5.6.3](#).

5.8.5 Birinapant Pharmacokinetics

5.8.5.1 Specimens and Processing

Upon receipt, frozen, processed plasma aliquots will be barcoded and banked in -80°C freezers until distribution for testing to the NCI Center for Cancer Research Clinical Pharmacology Program (see Section [5.6.1](#)).

5.8.5.2 Handling of Specimens

Upon arrival in the NCI Blood Processing Core (BPC), samples will be kept on wet ice until centrifugation at 1500 g for approximately 10 min at 4°C. Samples will be processed within one hour of sample collection. Plasma will be transferred into 1.8 mL Nunc cryovials and stored at -70°C until the time of analysis. If sufficient plasma volume, each sample will be split into equal volume aliquots.

All samples sent to the NCI Blood Processing Core ([name] Lab) will be barcoded, with data entered and stored in the Labmatrix utilized by the BPC. This is a secure program, with access to Labmatrix limited to defined BPC personnel, who are issued individual user accounts. Installation of Labmatrix is limited to computers specified by [name]. These computers all have a password restricted login screen. All [name] lab personnel with access to patient information are required to complete the Human Subjects Research course.

Labmatrix creates a unique barcode ID for every sample and sample box, which cannot be traced back to patients without Labmatrix access. The data recorded for each sample includes the patient ID, name, trial name/protocol number, time drawn, cycle time point, dose, material type, as well as box and freezer location. Patient demographics associated with the clinical center patient number are provided in the system. For each sample, there are notes associated with the processing method (delay in sample processing, storage conditions on the ward, etc.).

Sample bar-codes are linked to patient demographics and limited clinical information. This information will only be provided to investigators listed on this protocol, via registered use of the Labmatrix. It is critical that the sample remains linked to patient information such as race, age, dates of diagnosis and death, and histological information about the tumor, in order to correlate genotype with these variables.

Barcoded samples are stored in barcoded boxes in a locked freezer at either -20 or -80°C according to stability requirements. These freezers are located onsite in the BPC and offsite at NCI Frederick Central Repository Services in Frederick, MD. Visitors to the laboratory are required to be accompanied by laboratory staff at all times.

Access to stored clinical samples is restricted. Samples will be stored until requested by a researcher named on the protocol. All requests are monitored and tracked in Labmatrix. All researchers are required to sign a form stating that the samples are only to be used for research purposes associated with this trial (as per the IRB approved protocol) and that any unused samples must be returned to the BPC. It is the responsibility of the NCI Principal Investigator to ensure that the samples requested are being used in a manner consistent with IRB approval.

Following completion of this study, samples will remain in storage as detailed above. Access to these samples will only be granted following IRB approval of an additional protocol, granting the rights to use the material.

If, at any time, a patient withdraws from the study and does not wish for their existing samples to be utilized, the individual must provide a written request. Following receipt of this request, the samples will be destroyed (or returned to the patient, if so requested), and reported as such to the IRB. Any samples lost (in transit or by a researcher) or

destroyed due to unknown sample integrity (i.e. broken freezer allows for extensive sample thawing, etc.) will be reported as such to the CTEP.

5.8.5.3 Site Performing Correlative Study

NCI Center for Cancer Research Clinical Pharmacology Program (CPP)

5.8.5.4 Contact information for notification of specimen shipment

Refer to Section **5.6.1**.

5.8.6 Birinapant Pharmacogenomics (Single-nucleotide polymorphisms – SNPs)

5.8.6.1 Specimens and Processing

Upon receipt, EDTA blood samples will be barcoded and the buffy coat will be extracted. PBMCs of the buffy coat will be placed in media containing 10% DMSO and 90% FBS and then frozen in a -80degree freezer using a [name] isopropanol container.

PBMCs will be processed using a QiaAmp DNA blood kit. DNA will be extracted and SNP analysis will be run using the Pharmacoscan assay kit:

(<https://www.thermofisher.com/order/catalog/product/903010TS#/903010TS>).

Approximately 4500 SNPs in absorption, distribution, metabolism and excretion (ADME) genes will be evaluated.

5.8.6.2 Handling of Specimens

Upon arrival in the NCI Blood Processing Core, samples will be kept on wet ice until centrifugation at 1500g for approximately 10 minutes at 4°C. Samples will be processed within one hour of sample collection as described above.

All samples sent to the NCI Blood Processing Core will be barcoded, with data entered and stored in the Labmatrix utilized by the BPC. The handling procedure will be the same as described in Section **5.8.5.2**.

5.8.6.3 Site Performing Correlative Study

NCI Center for Cancer Research Clinical Pharmacology Program (CPP)

5.8.6.4 Contact information for notification of specimen shipment

Refer to Section **5.6.1**.

6 TREATMENT PLAN

This is an open-label Phase I study enrolling patients in 2 cohorts: dose escalation cohort and expansion cohort.

Treatment will be delivered in 2 cycles, lasting 3 weeks each.

Birinapant will be administered IV on Days 2 and 9 of each cycle in combination with IMRRT starting on Day 1 of cycle 1 and continuing for 5 days a week (Monday-Friday) for 6 weeks.

If a dose of birinapant is missed due to a scheduled holiday, inclement weather, personal emergency, or other reasons, then it should be given the following day.

If daily radiation treatment is missed due to a scheduled holiday, inclement weather, personal emergency, or other reasons, then the day(s) and fraction(s) missed should be added at the end of the course to complete the total planned treatment dose (e.g. 60Gy).

Patients in the dose escalation cohort will be treated with escalating doses of birinapant with IMRRT until MTD of birinapant in combination with IMRRT is established.

Patients in expansion cohort will be treated with the estimated MTD of birinapant in combination with IMRRT.

6.1 Agent Administration

Treatment will be administered primarily on an outpatient basis unless inpatient admission is indicated. Reported adverse events and potential risks are described in Section 10. Appropriate dose modifications are described in Section 7. No investigational or commercial agents or therapies other than those described below may be administered with the intent to treat the patient's malignancy.

6.1.1 Dose Escalation Cohort

Birinapant will be administered IV over 30 minutes on Days 2 and 9 of each 3-week cycle with starting dose 5.6 mg/m² per dose in combination with IMRRT starting on Day 1 of cycle 1 at 2Gy/day x 5 days/week/M-F for two cycles (6 weeks) to a total of 60-66Gy.

IMRRT will start within 1-4 hours after the infusion of birinapant.

Vital signs will be collected prior to and after every birinapant infusion.

An ECG will be performed within 2 hours prior to the start of infusion and 2 hours after infusion completion to evaluate for pre- and post-treatment abnormalities, including QT/QTc prolongation. Further continuous monitoring will be performed for ECG abnormalities following infusion until resolved.

After the first and second infusion of birinapant, patients will be observed for 30-60 minutes for adverse events.

Dose escalation (**Table 1**) will proceed in dose levels of 3–6 patients. The MTD is the dose level at which no more than 1 of up to 6 patients experience DLT during 42 days after the start of therapy, and the dose below that at which at least 2 (of ≤6) patients have DLT as a result of the drug.

Patients who have not received at least 80% of the total planned dose of birinapant and radiation therapy within the planned 42 days of treatment will not be evaluable for DLT assessment, even if they have not experienced any DLTs while receiving the treatment.

The first subject in each dose level group will be observed for at least 14 (+/-3) days after Cycle 2 radiation is completed before the second subject can be treated. If no DLT is observed within that period, the second patient can enroll. An interval of 14 (+/-3) days without a DLT must pass before treatment of the next patient, i.e. before treating patients within each dose cohort.

As of Amendment version date 12/15/2022, up to 3 patients may be enrolled in each remaining dose cohort (3 and 4). DLT observation periods noted in above paragraph are no longer required prior to enrolling subsequent patients.

A safety assessment for each dose cohort will be conducted 14 days (+/- 3 days) after the last

patient of each dose cohort has completed treatment. If no DLTs are observed for the specific dose cohort, enrollment in the next dose cohort can proceed, following approval by the Medical Monitor.

The study team will meet weekly to review the ongoing results of the trial during the dose escalation portion of the study.

Dose levels are defined in the table below. Starting dose will be 5.6 mg/m². If >1/6 patients develop a DLT at level 1 dose and a maximum 1/6 patients develop a DLT at the level -1 dose, the latter will be determined as the MTD.

Table 1: Dose Escalation Schedule

Dose Level	Birinapant (mg/m ²)
Level -1	2.8
Level 1	5.6
Level 2	11
Level 3	17
Level 4	24

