No more than 1% or 1 cc of tissue outside the PTV will receive > 110% of the dose prescribed to the PTV.

The dose prescription will be based on dose distribution corrected for tissue inhomogeneity.

PTV 60 Gy will include the primary tumor and involved nodal regions if adjacent nodal regions have disease or are at high risk. 1-2 levels of lymph nodal levels can be treated at the discretion of the radiation oncologist and based on imaging data (CT, PET/CT and/or MRI). The dose in this region can go as high as 66 Gy as long as the normal structure tolerances are met.

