6.1.2.5 Suggested Dose restraints for critical normal structures

For CNS structures, Brainstem, Optic nerve and Optic chiasm: No more than 0.03 cc can exceed 60 Gy (from current AND previous radiation therapy treatments combined). Mandible: There are no specific requirements for brachial plexus dose, but if it is not grossly involved with or immediately adjacent to tumor, the dose should be kept as low as reasonably possible. Minimize hot spots.

Brachial plexus: There are no specific requirements for brachial plexus dose, but if it is not grossly involved with or immediately adjacent to tumor, the dose should be kept as low as reasonably possible. Minimize hot spots.

Larynx: There are no specific requirements for larynx dose, but if it is not grossly involved with or immediately adjacent to tumor, the dose should be kept as low as reasonably possible. Minimize hot spots.

6.1.2.6 Treatment Delivery/ Equipment:

Megavoltage equipment capable of delivering static-gantry intensity modulation beams with a multi-leaf collimator or dynamic intensity modulation (using a multi-leaf collimator or tomotherapy) is required. Other techniques are acceptable as long as dose specifications and constraints are satisfied. This includes tomotherapy and Volumetric Modulated Arc Therapy (VMAT) techniques. It is expected that the entire treatment of definitive irradiation will be completed in approximately seven weeks. Radiation course should be continuous (Monday-Friday) for 5 days. However, if an interruption is required for radiation reaction, it should be kept to a minimum, recorded, and justified.

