6.2 Definition of Dose-Limiting Toxicity

Dose-limiting toxicity (DLT) will be defined as any one of the following adverse events, possibly attributable to the combination of birinapant and radiotherapy, that occur within 42 days of the start of therapy:

- Any grade 5 toxicities.

- Any grade ≥ 4 hematologic toxicity except for lymphopenia.
- Any grade ≥ 3 non-hematologic toxicity, **except for any of the following:**
 - nausea and vomiting that can be managed with standard supportive care over 2 weeks
 - alopecia,
 - drug-related fever,
 - radiation-induced in-field related side effects, including but not limited to dermatitis, oral mucositis and related pain, dysphagia, dysgeusia, esophagitis, xerostomia, weight loss, thickened oral secretions that can be managed with standard supportive care over 2 weeks
 - isolated laboratory abnormalities without clinical sequelae
- \geq grade 3 prolonged (> 7 days) serum amylase or lipase elevation*
- \geq grade 3 prolonged (> 7 days) aspartate aminotransferase (AST) elevation*
- \geq grade 3 prolonged (> 7 days) alanine aminotransferase (ALT) elevation*
- Concurrent elevation of AST/ALT > 3 times the upper limit of normal and bilirubin > 2 times the upper limit of normal (i.e., Hy's law)
- Any grade toxicity that mandates discontinuation of birinapant treatment for more than 2 weeks

* all of which will be considered to be dose limiting.

Grade 5 AEs are unacceptable, though the chances of their occurrence are considered to be quite low. The probability of DLTs with birinapant in combination with radiotherapy at the specified dose levels are expected not to exceed 30% of patients. All AEs \leq grade 4 are considered acceptable in terms of risk, given that the median overall survival of patients with locoregionally recurrent head and neck cancer who have received 1 or 2 lines of standard of care treatment is very short (approximately 3-6 months).

Criteria are based on the NCI Common Terminology Criteria for Adverse Events, Version 5.0.

Dose escalation will proceed within each dose level according to the following scheme. Dose-limiting toxicity (DLT) is defined above.

Number of Patients with DLT at a Given Dose Level	Escalation Decision Rule
0 out of 3	Enter 3 patients at the next dose level.

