6.3 Dose Expansion Cohort

Birinapant will be administered IV over 30 minutes on days 2 and 9 of every cycle at the MTD estimated during dose escalation part of the study.

IMRRT will be administered starting on Day 1 at 2Gy/day x 5 days/week/M-F for 2 cycles (6 weeks) to a total of 60-66Gy.

IMRRT will start within 1-4h after the infusion of birinapant.

The study team will meet weekly to review the ongoing results of the trial and will continue to monitor and record AEs during the dose expansion portion of the study.

An expansion cohort of 10 additional patients will be treated at the MTD and the results combined with those of patients at the MTD to obtain improved estimates of safety and toxicity as well as to perform analyses to address secondary objectives.

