11 STUDY CALENDAR

A time window of -2 days on treatment days and +/- 2 days on non-treatment days will be permitted for weekly physical exam, performance status, routine vital signs, weight and routine labs. Cycle days will be numbered relative to treatment.

Procedure/ Assessment	Screening	Baseline	C1D1 Wk1	C1D2 Wk1	C1D4 Wk1	C1D8 Wk2	C1D9 Wk2	C1D15 Wk3	C2D1 Wk4	C2D2 Wk4	C2D8 Wk5	C2D9 Wk5	C2D15 Wk6	14 Day Safety Visit j, 1	28 Day Post tx Safety Visit j, 1	Long term Follow Up k,1
Informed consent	X	X														
Birinapant ^a						X ^c										
Re-IMRT ^b			X	X	X	X	X	X	X	X	X	X	X	X	X	
Demographics	X															
Medical history	X															
Concurrent meds	X		X				X	X				X		X	X	X ^p
Physical exam ^q	X		X				X	X				X		X	X	
Vital signs	X		X	X ^d		X	X ^d	X	X	X ^d	X	X	X	X	X	
Height		X														
Weight		X	X								X			X	X	
Performance status	X		X								X			X	X	
CBC/diff, platelets	X		X				X	X			X		X	X	X	
Serum chemistry ^e	X		X			X	X	X			X		X	X	X	
PT/PTT/INR	X															
HIV test	X															
ECG ⁿ	X					X					X					
Adverse events		X					X	X			X		X	X	X	
Tumor biopsy f,r		X				X										

Procedure/ Assessment	Screening ≤ 4 weeks of first treatment	Baseline	C1D1 Wk1	C1D2 Wk1	C1D4 Wk1	C1D8 Wk2	C1D9 Wk2	C1D15 Wk3	C2D1 Wk4	C2D2 Wk4	C2D8 Wk5	C2D9 Wk5	C2D15 Wk6	14 Day Post tx Safety Visit j, 1	28 Day Post tx Safety Visit j, 1	Long term Follow Up k, 1
Blood (for control DNA) ^r		X														
Urine HCG ^g	X		X													
Tumor measurements ^h	X															X
Blood for Pharmacokinetics																
Blood for Pharmacogenomics																
Phone call or e-mail																X
Dental Evaluation		X														

- a: Birinapant on days 2 and 9 of every cycle. If a patient misses a dose on each of those days, the infusion can be given up to 2 days later, but the C1D4 biopsy will not be performed.
- b: Standard re-IMRT 2GY/day/5 days a week/ M-F for 6 weeks to 60-66Gy.
- c: Patients will be observed for 30-60 minutes post the first and second infusion of birinapant for adverse events.
- d: Vital signs will be collected prior to and after every birinapant infusion.
- e: Albumin, alkaline phosphatase, total bilirubin, bicarbonate, BUN, calcium, chloride, creatinine, glucose, LDH, phosphorus, potassium, total protein, SGOT [AST], SGPT [ALT], sodium, magnesium, uric acid, amylase, lipase.

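### The stated radiation schedule (2 Gy, 5 days a week, 6 weeks) delivers 60 Gy, not 60-66 Gy; courses above 60 Gy run past day 42 and meet the DLT window and the 80% evaluability rule differently

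*Combined protocol and SAP*

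**What the plan says.** **Schedule and total dose.** Section 6.1.1 (escalation) gives "2Gy/day x 5 days/week/M-F for two cycles (6 weeks) to a total of 60-66Gy". Section 6.3 (expansion) has "2Gy/day x 5 days/week/M-F for 2 cycles (6 weeks) to a total of 60-66Gy", and footnote b of the Study Calendar has "Standard re-IMRT 2GY/day/5 days a week/ M-F for 6 weeks to 60-66Gy". Section 6.1.2.4 sets a 60 Gy planning volume and adds: "The dose in this region can go as high as 66 Gy as long as the normal structure tolerances are met".

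**Duration.** Section 6 says "Treatment will be delivered in 2 cycles, lasting 3 weeks each", with radiation five days a week for six weeks. For missed radiation days it says "then the day(s) and fraction(s) missed should be added at the end of the course to complete the total planned treatment dose". Section 6.1.2.6 says "It is expected that the entire treatment of definitive irradiation will be completed in approximately seven weeks". The calendar's last on-treatment column is C2D15, week 6.

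**Rules tied to 42 days.** Section 6.2 counts DLTs "that occur within 42 days of the start of therapy", and the MTD definition in Section 6.1.1 uses the same 42 days. Section 6.1.1 also requires at least 80% of the planned birinapant and radiation dose within the planned 42 days for a patient to be evaluable for DLT. Section 9.2 instead describes a DLT evaluation period of 42 days plus 14 (+/- 3) days of follow-up.

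**The concern.** The daily dose, days per week and weeks multiply to the bottom of the stated dose range only. A site prescribing more than 60 Gy cannot keep to both 2 Gy per fraction and six weeks, and the two statements of duration disagree.

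This matters statistically because the primary endpoint is counted against a fixed 42 days. If permitted courses differ in length, a fixed window and a fixed exposure deadline do not treat patients alike. Dose-level decisions rest on 3 to 6 patients, so whether one patient is evaluable, or one late event is counted, can change an escalation step.

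**Working it through.** **Inputs.** 2 Gy per fraction, 5 fractions a week, 6 weeks, total 60-66 Gy (Sections 6.1.1 and 6.3, calendar footnote b); 42-day DLT window (Sections 6.1.1 and 6.2); 42 + 14 (+/- 3) days (Section 9.2); 80% of planned dose within 42 days (Section 6.1.1).

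**Step 1: reproduce the stated total.** Dose = Gy per fraction x fractions per week x weeks = 2 x 5 x 6 = 60 Gy in 30 fractions. Only the lower end of 60-66 Gy is reproduced. Fitting 66 Gy into 30 fractions would need 66/30 = 2.2 Gy per fraction, against the stated 2 Gy. Seven full weeks would hold 2 x 5 x 7 = 70 Gy, so the duration in Section 6.1.2.6 has room for 66 Gy.

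**Step 2: course length and the 80% rule.** Fractions = total/2. The last day assumes a Monday start, one fraction per weekday and no missed days. Days 1 to 42 contain 30 weekdays, so at most 30 fractions can be given by day 42. Missed fractions are added at the end of the course, so they cannot be recovered before then. Fractions needed = 0.8 x planned fractions, rounded up; tolerated misses = 30 minus that number.

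| Planned total | Fractions | Last day | Most deliverable by day 42 | Needed for 80% | Missed days tolerated |
|---|---|---|---|---|---|
| 60 Gy | 30 | 40 | 30/30 = 100% | 24 | 6 |
| 62 Gy | 31 | 43 | 30/31 = 96.8% | 25 | 5 |
| 64 Gy | 32 | 44 | 30/32 = 93.8% | 26 | 4 |
| 66 Gy | 33 | 45 | 30/33 = 90.9% | 27 | 3 |

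With a Tuesday start the 60 Gy course ends on day 42; the longer courses still end on days 43 to 45.

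**Step 3: same delivery, different status.** Two patients each miss four treatment days, so each has had 26 fractions (52 Gy) by day 42. On a 60 Gy plan, 26/30 = 86.7%, and the radiation criterion is met. On a 66 Gy plan, 26/33 = 78.8%, and it is not.

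**Step 4: DLT window.** An uninterrupted 60 Gy course lies wholly inside 42 days. Fractions 31 to 33 of a 66 Gy course, on days 43 to 45, lie outside it. The Section 9.2 period runs to between day 42 + 11 = 53 and day 42 + 17 = 59, so it includes them. A qualifying toxicity on day 44 is therefore a DLT under Section 9.2 and not under Sections 6.1.1 and 6.2.

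**The case against.** The strongest reply is that this is a wording conflict with little consequence. Several parts of that reply stand.

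- **The treatment plan is not silent on a seventh week.** A reader might infer that it is. Section 6.1.2.6 lies within the treatment plan and expects about seven weeks, and Section 6 lets the course lengthen for missed fractions. The fault is contradiction. The extension in Section 6 concerns missed fractions, though, not planned fractions 31 to 33.
- **The choice of 60 or 66 Gy is not expressly left to the radiation oncologist.** In Section 6.1.2.4 that discretion concerns treating one or two nodal levels; going up to 66 Gy is conditional on normal-structure tolerances.
- **Confounding of the MTD is not shown.** With the same number of missed days, 60 Gy and 66 Gy patients treated at 2 Gy have received the same dose by day 42, so the extra 6 Gy cannot affect DLTs counted in the 42-day window. It could matter only under Section 9.2. The last birinapant dose is on study day 21 + 9 = 30, which is 13 to 15 days before the extra fractions. With the 52-hour tumor half-life in Section 2.2, 13 days is 312/52 = 6 half-lives. Section 6.2 also exempts in-field radiation effects that supportive care can manage over two weeks.
- **The 80% rule can still be met at 66 Gy**, since 90.9% is deliverable by day 42.
- **Follow-up is not lost.** The 14- and 28-day visits and the cohort safety assessment are counted from completion of treatment.

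None of this makes the schedule multiply out, removes the conflict between the DLT windows, or equalizes the margin for missed days.

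**Conclusion.** The point holds as an internal inconsistency that reaches the rules for counting DLTs. The stated schedule gives 60 Gy. Totals above that need one to three further fractions, ending on days 43 to 45, and agree with only one of the two stated durations. Two consequences follow: up to three fractions fall outside one stated DLT window and inside the other, and the allowance for missed treatment days halves from 6 to 3 between a 60 Gy and a 66 Gy plan.

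This rests on 2 Gy per fraction throughout, one fraction per weekday, and reading planned dose in the 80% rule as the individual patient's prescribed dose. The documents do not say how many patients are prescribed more than 60 Gy. If none are, the effect on counting is nil and only the wording is wrong. The calendar finding rests on its column headings alone, because the table body is broken in the available text. It does not follow that the MTD estimate is biased by radiation dose.

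**What to change.** 1. Reconcile Sections 6, 6.1.1, 6.1.2.4, 6.1.2.6 and 6.3 and calendar footnote b so that dose per fraction, number of fractions, total dose and weeks agree for every permitted course. Which courses are permitted is for the sponsor to decide.
2. Reconcile the DLT window in Sections 6.1.1 and 6.2 with the period in Section 9.2, so that one window applies and treats every permitted course alike.
3. In the 80% rule, define planned treatment time from the patient's own prescription in place of a fixed 42 days.
4. Align the calendar's on-treatment columns with the longest permitted course.
5. As an inexpensive addition, not the correction of an error, list DLTs by birinapant level and delivered radiation dose.

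The cost is amendment wording, possibly one calendar column, and one extra listing. Sample size and the 3+3 rules are unchanged.

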9.2 Sample Size/ Accrual Rate

This trial will initially consist of a 4 dose levels 3+3 escalation phase; with up to 6 patients per dose level, up to 24 patients may be required to determine the MTD. Then, at the MTD, an additional 10 patients will be treated in order to determine more precise estimates of safety and toxicity of patients as well as to address secondary objectives. If there are 16 patients at the MTD including the expansion cohort, then there would be approximately 80% power to detect an effect size of 2.0 for a given test comparing two groups or comparing pre-treatment values to on-treatment values with a 1.0 effect size, with a 0.01 two-tailed significance test. This would be sufficient to allow for up to 6 tests to be performed while holding the overall significance level to 0.05, taking into consideration enough patients to allow for a Bonferroni correction. In practice, given the exploratory nature of the marker and related analyses, the results may be presented without any such formal correction, but in the context of the number of such tests performed. As an illustration, if IAP1, CASP3, and MLKL were each obtained pre-treatment and at day 4 on treatment, with 16 total patients at the MTD, there would be adequate patients so that the

differences could each be tested with at least 80% power with an effect size equal to 1.0 times the standard deviation of the difference, with a 0.01 two-tailed significance test. In addition, although with less power depending on the fraction of patients who respond, comparisons could be made of the changes in these parameters between patients who respond or do not respond.

If all dose levels are evaluated and 10 additional patients are included at the MTD, we anticipate enrolling a minimum of 16 patients and a maximum of 34 patients. It is anticipated that 1-2 patients/month may be enrolled onto this trial.

Primary endpoints will be the DLTs and other toxicities, and the MTD for the regimen.

For DLT and MTD determination, escalation will proceed with the 3+3 dose escalation design until either the stopping rule below or the MTD is reached.

No. of patients with DLT's at this dose level	No. of patients treated at this dose level	Action
Dose escalation rules		
0	3	Treat 3 patients at the next higher dose level (or add 3 patients if at the highest level).
1	3	Treat 3 additional patients at this dose level.

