1	6	Treat 3 patients at the next higher dose level (or if at the highest level, declare the dose at this level to be the MTD).
>1	3 or 6	Stop dose escalation; begin dose de-escalation. De-escalate one dose level.

The DLT evaluation period between dose levels will be 42 days during drug/radiation treatment plus 14 (+/- 3) days of follow-up thereafter. Patients are considered evaluable for toxicity if they have received at least 1 dose of birinapant. Patients that are not evaluable will be replaced. A standard “3+3” design, described in the table below, will be followed.

PLANNED ENROLLMENT REPORT

Racial Categories	Ethnic Categories					Total
	Not Hispanic or Latino		Hispanic or Latino			
	Female	Male	Female	Male		
American Indian/ Alaska Native	0	0	0	0		0
Asian	0	2	0	0		2
Native Hawaiian or Other Pacific Islander	0	0	0	0		0
Black or African American	1	3	0	2		6
White	5	19	0	1		25
More Than One Race	0	1	0	0		1
Total	6	25	0	3		34

PHS 398 / PHS 2590 (Rev. 08/12 Approved Through 8/31/2015)

OMB No. 0925-0001/0002

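### The 80% exposure rule for DLT evaluability in 6.1.1 makes no exception for patients who had a DLT, and 9.2 does not say which definition of evaluable triggers replacement

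*Combined protocol and SAP*

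**What the plan says.** Section 6.1.1 sets the evaluability rule. It describes the group concerned as "Patients who have not received at least 80% of the total planned dose of birinapant and radiation therapy within the planned 42 days". The stated consequence for this group is that they "will not be evaluable for DLT assessment, even if they have not experienced any DLTs while receiving the treatment". The same section defines the target of the escalation ("The MTD is the dose level at which no more than 1 of up to 6 patients experience DLT during 42 days") and the gate between cohorts ("If no DLTs are observed for the specific dose cohort, enrollment in the next dose cohort can proceed, following approval by the Medical Monitor").

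Section 9.2, just after the 3+3 table, first gives the window: "The DLT evaluation period between dose levels will be 42 days during drug/radiation treatment plus 14 (+/- 3) days of follow-up thereafter". It then says: "Patients are considered evaluable for toxicity if they have received at least 1 dose of birinapant. Patients that are not evaluable will be replaced". Section 12.1.1 uses the same first-dose threshold for toxicity in general.

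The handling of a DLT is set elsewhere:
- Section 6.2 lists any grade 5 toxicity, and any toxicity that keeps birinapant off for more than 2 weeks, as DLTs.
- Section 7.1.2 holds both treatments for up to 2 weeks after a combination-related DLT, then resumes birinapant one level lower. Hy's-law cases stop study treatment for good.
- Section 6 adds missed radiation fractions at the end of the course.
- Section 6.5 equates less than 80% of birinapant doses with fewer than 3 of 4.

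**The concern.** The words after the comma in the 6.1.1 rule extend the exclusion to DLT-free patients. They do not limit it to them. As written, a patient whose DLT caused the shortfall is also non-evaluable for DLT assessment, and 9.2 replaces non-evaluable patients.

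A DLT, and the way the protocol handles it, lowers exposure. The rule can therefore remove the very events that the 3+3 design exists to count. DLTs and the MTD are the primary endpoint, dose cohorts 3 and 4 remain, and 10 expansion patients are treated at the dose that results. If DLT patients are replaced more often than DLT-free patients, the counted DLT rate is too low and the MTD tends to be set too high.

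**Working it through.** **The plan's own figures.** Section 9.2 gives up to 24 patients for escalation and 16 to 34 in total. These reproduce: 4 × 6 = 24, 24 + 10 = 34, 6 + 10 = 16. They hold no allowance for replacements, and none of them is in dispute.

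**Can a DLT patient fall below 80%?** Inputs: birinapant on Days 2, 9, 23 and 30; 2 Gy per fraction, so 30 fractions for 60 Gy and 33 for 66 Gy; 30 weekdays in 42 days. Assumption: falling short on either component fails the rule.

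- Radiation, with the whole hold of h fractions inside the 42 days: (30 − h)/30 at 60 Gy and (30 − h)/33 at 66 Gy. At 60 Gy, h = 6 gives 80.0%, h = 7 gives 76.7% and h = 10 gives 66.7%. At 66 Gy, h = 3 gives 81.8%, h = 4 gives 78.8% and h = 10 gives 60.6%. (A cumulative break of 10 business days also ends protocol therapy under 7.2.)
- Radiation ended by a grade 5 toxicity before fraction 24 (Day 32 with a Monday start, 60 Gy): at most 23/30 = 76.7%. Once fraction 24 has been given, 60 Gy patients cannot fall below 80%.
- Birinapant by total mg: 80% of 4 doses is 3.2, so a permanent stop before dose 4 leaves at most 3/4 = 75%.
- Birinapant by total mg, one level lower after dose 1, (full + 3 × lower)/(4 × full): level 1 (5.6 + 8.4)/22.4 = 62.5%; level 2 (11 + 16.8)/44 = 63.2%; level 3 (17 + 33)/68 = 73.5%; level 4 (24 + 51)/96 = 78.1%. After dose 2 the figures are 75.0%, 75.5%, 82.4% and 85.4%, so at levels 3 and 4 only a reduction after dose 1 fails.
- Birinapant by dose count as in 6.5: only a stop before dose 3 (Day 23) fails, at 2/4 = 50% or less.

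**Effect on the 3+3 count.** Let p be the true DLT rate, f the share of DLT patients replaced and g the share of DLT-free patients replaced. The documents give neither f nor g.

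- Counted rate: q = p(1 − f)/[p(1 − f) + (1 − p)(1 − g)]. If f = g, then q = p and there is no bias.
- Chance of clearing a level (0 of 3, or 1 of 3 then 0 of 3): (1 − q)³ + 3q(1 − q)⁵.
- Example, p = 0.30, f = 0.50, g = 0: q = 0.15/0.85 = 0.176; 0.8235³ + 3 × 0.1765 × 0.8235⁵ = 0.559 + 0.201 = 0.759.

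| Chance of clearing a level | f = 0 | f = 25% | f = 50% | f = 75% |
|---|---|---|---|---|
| p = 30%, g = 0 | 0.494 | 0.614 | 0.759 | 0.911 |
| p = 30%, g = 10% | not computed | 0.572 | 0.725 | 0.895 |
| p = 20%, g = 0 | 0.709 | 0.798 | 0.887 | 0.964 |

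The 30% is the ceiling that 6.2 expects for the DLT probability.

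**Remaining trial.** At level 4, 9.2 adds 3 patients after 0 of 3, so the level passes with at most 1 of 6: (1 − q)⁶ + 6q(1 − q)⁵. At p = 30% and g = 0 this is 0.420, 0.550, 0.713 and 0.892 for f = 0, 25%, 50% and 75%. With assumed rates of 20% at level 3 and 30% at level 4, the chance that level 4 is declared the MTD is the product, for example 0.709 × 0.420 = 0.298 at f = 0. For f = 25%, 50% and 75% it is 0.439, 0.633 and 0.860 with g = 0, and 0.386, 0.585 and 0.835 with g = 10%.

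**The case against.** The strongest reply is that nobody would apply the rule this way. The clause about DLT-free patients reads as a safeguard against counting under-exposed patients as safe. Several sections agree. Section 6.2 makes death and long discontinuation DLTs. Section 7.1.2 leaves re-treated patients out of the count only at the lower level, which implies that they count where they were assigned. The 9.2 table counts patients treated. The primary analysis, placed under 9.3, reports the DLTs obtained at each level with no exposure filter. The gate in 6.1.1 asks only whether DLTs were observed, and Medical Monitor approval and Principal Investigator sign-off stand in the way of discarding a death. This carries weight. It makes f = 0 the likely intent, and with g = 0 that means no bias. It does not supply the missing sentence, and approval steps do not define a count.

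The single-component routes also depend on reading the rule as failed when either component is short. If both must be short, those routes go. A death before dose 3 on Day 23 would still qualify: at most 2/4 = 50% of doses and, with a Monday start, at most 16/30 = 53.3% of 60 Gy.

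A reader might infer two stronger things. One is that 9.2 sets up a rival one-dose rule for the DLT count. The documents do not support this. Section 9.2 speaks of evaluability for toxicity, the same term and threshold as 12.1.1, and both can stand as the general safety set. What remains unclear in 9.2 is which patients the replacement sentence refers to. The other is that DLTs have already been dropped. Nothing shows this. The amendment cover letter reports no DLT that required 3 more participants at either of the first two levels, and the documents do not say whether anyone was replaced there.

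**Conclusion.** The 6.1.1 rule is wrong as written and should be fixed, though the defect is most likely one of wording. Followed exactly, it allows DLT patients to leave the 3+3 count and be replaced, and selective replacement of that kind biases the MTD upward.

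The size is an illustration. At a true rate of 30% and g = 0, replacing 25% to 75% of DLT patients moves the chance of clearing a level from 49% to between 61% and 91%. This rests on literal application, on either component being enough to fail, and on assumed values of f and g. Setting g = 0 gives the largest effect; g = 10% gives 57% to 90%. The point does not rank above a clarification, because the rest of the protocol suggests that such DLTs are meant to count.

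**What to change.** - In 6.1.1, state that any patient with at least one birinapant dose who has a DLT in the DLT window counts at the assigned level, whatever exposure was received, and that the 80% threshold applies only to DLT-free patients.
- In 9.2, state that replacement applies only to patients who are non-evaluable under that rule. Label the one-dose definition in 9.2 and 12.1.1 as the general toxicity set.
- Report the number replaced at each level with reasons, including levels 1 and 2.
- Reconcile two pairs of passages on which the count depends: the DLT window (42 days in 6.1.1 and 6.2; 42 plus 14 days in 9.2) and the meaning of 80% (total planned dose in 6.1.1; fewer than 3 of 4 doses in 6.5, where 3 of 4 is 75%). No view is taken on which is right.

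The 80% threshold is worth keeping for DLT-free patients. If a one-dose rule governed the count, and a share d of patients left early and counted as DLT-free, the counted rate at p = 30% would be p(1 − d): 0.27 for d = 10% and 0.24 for d = 20%. The chance of clearing would be 0.557 and 0.622 against 0.494. The proposed rule sets f = 0; with g = 10% the counted rate is 0.30/(0.30 + 0.70 × 0.90) = 0.323, a small error on the cautious side.

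Cost: a wording amendment. No visits or data are added, and no patients beyond the replacements that 9.2 already allows.
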